2.5 DATA HANDLING CONVENTIONS

2.5.1 Conventions

The following formulas will be used for computation of parameters.

Time since event / duration

Time since [event]/duration (years) = (Date of informed consent – Date of [event]¹) / 365.25.

[event] can be quit smoking, menopause. Duration can be for diabetes, hypercholesterolemia, insulin use, hypertension...

Date of last dose of IMP

The date of the last injection is equal to the last date of administration reported on injection administration e-CRF page, or missing if the last administration date is unknown.

HbA1c formula

The master equation for converting National Glycohemoglobin Standardization Program (NGSP) units into International Federation of Clinical Chemistry (IFCC) units (8) is:

HbA1c mmol/mol = 10.93 x HbA1c% - 23.5

Renal function formulas

Estimated GFR (estimated Glomerular Filtration Rate) value will be derived using the Modification of Diet in Renal Disease (MDRD) equation:

$186.3 \times (\text{creatinine in } \mu\text{mol/L} / 88.4)^{-1.154} \times (\text{age in years})^{-0.203}$ (x 0.742 if female, x 1.21 if race is "black or african american").

Lipids variables and laboratory safety variables

For data below the lower limit of quantification (LLOQ)/limit of linearity, half of the lower limit value (ie, LLOQ/2) will be used for quantitative analyses. For data above the upper limit of quantification (ULOQ)/limit of linearity, the upper limit value (ie, ULOQ) will be used for quantitative analyses.

2.5.2 Data handling conventions for secondary efficacy variables

See [Section 2.4.5.2](#).

¹ In case the month of event would be missing, it will be put equal to JANUARY if the year of event equals the year of informed consent; it will be put equal to JULY otherwise. In case the day of event would be missing, it will be put equal to 1.

2.5.3 Missing data

For categorical variables, patients with missing data are not included in calculations of percentages unless otherwise specified. When relevant, the number of patients with missing data is presented.

Handling of baseline definition if time of first double-blind administration or time of assessment at Week 0 visit is missing

If the time of the first double-blind administration or time of assessment at Week 0 visit is missing then the baseline value is defined as the last available value obtained before (ie, at an unscheduled visit) or on the day of the first double-blind IMP administration.

Handling of computation of treatment duration if investigational medicinal product first or end of treatment date is missing

If the last or first injection date is missing, the exposure duration and compliance will be left as missing.

Handling of safety and efficacy analysis periods and survival analysis if investigational medicinal product end of treatment date is missing

If the last injection date is missing, then this date is imputed to the earliest between:

- The last day of the month and year, when applicable or else the 31st of December of the year;
- The date of the end of treatment visit (Week 24 visit for completer, early end of treatment visit for patients who prematurely discontinued the IMP);
- And the date of the last contact;

for the purpose of safety and efficacy analysis period start and/or end.

Handling of medication missing/partial dates

No imputation of medication start/end dates or times will be performed. If a medication date or time is missing or partially missing and it cannot be determined whether it was taken prior or concomitantly, it will be considered a prior, concomitant, and post-treatment medication.

Handling of adverse events with missing or partial date/time of onset

Missing or partial AE dates and times will be imputed so that if the partial AE date/time information does not indicate that the AE started prior to treatment or after the TEAE period, the AE will be classified as treatment-emergent. These data imputations are for categorization purpose only and will not be used in listings. No imputation is planned for date/time of AE resolution.

Handling of adverse events when date and time of first investigational medicinal product administration is missing

When the date and time of the first IMP administration is missing, all AEs that occurred on or after the day of randomization will be considered as TEAEs.

When the time of the first double-blind IMP administration is missing, all AEs that occurred on the day of the first double-blind IMP administration will be considered as treatment-emergent AEs.

Handling of missing assessment of relationship of adverse events to investigational medicinal product

If the assessment of the relationship to IMP is missing, then the relationship to IMP has to be assumed as possibly related in the frequency tables, but no imputation should be done at the data level.

Handling of potentially clinically significant abnormalities

If a patient has a missing baseline value he will be grouped in the category “normal/missing at baseline.”

For PCSAs with two conditions:

- The first one based on a change from baseline value
- The other one based on a threshold value or a normal range,

If the first condition is missing, PCSA will be only based on the second condition.

For a PCSA defined on a threshold value and/or a normal range, it will be derived using this threshold if the normal range is missing; eg, for eosinophils, if no ULN is available or if ULN is <0.5 GIGA/L then the PCSA is >0.5 GIGA/L, while if ULN is available and ≥ 0.5 GIGA/L then the PCSA is $>$ ULN.

Measurements flagged as invalid by the laboratory will not be summarized or taken into account in the computation of PCSA values.

[REDACTED]

[REDACTED]

2.5.4 Windows for time points

Data analyzed by time point (including efficacy, laboratory safety data, vital signs, [REDACTED] ADA) will be summarized using the analysis windows given in [Table 2](#). These analysis windows will be applicable for all analyses, and they are defined to provide more homogeneous data for time point-specific analyses.

Table 2 - Analysis windows definition

Time point	Targeted study day	Analysis window in study days
Week 4	29	15 to 42
Week 8	57	43 to 70
Week 12	85	71 to minimum (98; study day corresponding to the first injection with IMP from kit allocated at up-titration IVRS contact)
Week 20	141	127 to 154
Week 24	169	155 to 182
Week 32	225	211 to 238

Study days are calculated from the day of first double-blind IMP, the day of first double-blind injection being Day 1. For randomized but not treated patients, Day 1 is the day of randomization.

If multiple valid values of a variable exist within an analysis window, the nearest from the targeted study day will be selected. If the difference is a tie, the value after the targeted study day will be used. If multiple valid values of a variable exist within a same day, then the first value of the day will be selected when time is available, else the scheduled visit will be selected.

2.5.5 Unscheduled visits

For efficacy, safety laboratory data, or vital signs, unscheduled visit measurements may be used to provide a measurement for a time point, a baseline, a last or a worst value, if appropriate according to their definitions. The measurements may also be used to determine abnormal/PCSA.

2.5.6 Pooling of centers for statistical analyses

Not applicable.

2.5.7 Statistical technical issues

Not applicable.

3 INTERIM ANALYSIS

No formal interim analysis for efficacy is planned since analysis of primary and key secondary efficacy endpoints will be final at the time of first-step analysis described below. All efficacy data will be available for final analysis at a cut-off date corresponding to the Week 24 visit of the last patient, and both the efficacy and safety analyses will be performed in a first-step analysis. Since safety data are collected until the end of the study (Week 32), an update of the safety analysis will be performed in a second-step analysis at the end of the study.

The first-step analysis will be conducted as soon as all patients have been randomized and have at least all their data up to Week 24 analysis window collected and validated. It will consist of a final analysis of the primary and secondary efficacy endpoints up to Week 24, as well as safety analysis performed on all safety data collected up to the common cut-off date, defined as the date of the last Week 24 visit.

The second-step analysis will be conducted at the end of the study and will consist in the updated analysis of safety endpoints until Week 32. No multiplicity adjustment for multiple analyses is needed because all efficacy analyses will be completed at the time of the first-step analysis. Selected individuals who are not involved in the conduct of the study after the first step analysis will perform the second step analysis; individual patient identification will not be released to anyone who is directly involved in the ongoing conduct of the study.

Analyses methods and conventions described in the other sections of this SAP will be applied for all analyses as applicable. The following additional rules will apply for analyses performed at first step analysis:

- Any lipid assessments within analysis windows up to Week 24 will be taken into account (may include few unscheduled lipid data soon after the cut-off date).
- Patients without end of treatment visit performed at the time of the cut-off date will be considered as ongoing and exposed up to the cut-off date. Therefore:
 - Patients who did not complete treatment period nor prematurely discontinued the study treatment at cut-off date will be analyzed as “ongoing” in the disposition summary;
 - Their TEAE period, treatment period and on-study observation period will end at the cut-off date;
 - Their treatment duration will be derived by considering date of cut-off as last injection date and last capsule date.
- Analyses of number of injections, mean injection frequency, percentage of days with under/above-planned dosing and compliance (for injections and capsules) will be performed up to the last injection and capsule reported in the e-CRF up to the cut-off date.
- AEs occurring, worsening or becoming serious after the cut-off date will not be included in the analyses. However, any available outcome before database lock, regardless of timing in relation to the cut-off date, of an AE starting prior to the cut-off date will be taken into account. Medications, treatment discontinuations/completions, and deaths occurring after the cut-off date will not be included in the analyses.

- Post-treatment period, post-study period are not applicable for ongoing patients. Analyses of post-treatment AEs, post-study deaths, and post-treatment medications will be performed for patients who either completed or prematurely discontinued the treatment before or at the cut-off date.
- Analysis of status at last study contact and proportion of patients with insufficient follow-up will be provided for patients who either completed or prematurely discontinued the treatment before or at the cut-off date.

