10.3.5 Procedure and consequence for patient withdrawal from study

The patients may withdraw from the study before study completion if they decide to do so, at any time and irrespective of the reason.

If possible, the patients are assessed using the procedure normally planned for the EOT visit.

For patients who fail to return to the site, the Investigator should make the best effort to recontact the patient (eg, contacting patient's family or private physician, reviewing available registries or health care databases), and to determine his/her health status, including at least his/her vital status. Attempts to contact such patients must be documented in the patient's records (eg, times and dates of attempted telephone contact, receipt for sending a registered letter).

The statistical analysis plan will specify how the primary endpoints of patients who are lost to follow-up will be considered.

Patients who have withdrawn from the study cannot be rerandomized (treated) in the study. Their inclusion and treatment numbers must not be reused.

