Non continuous variables included in the imputer's model (ie, treatment group and gender) are not expected to be missing.

Pattern mixture model (see Appendix D for more details):

Multiple imputations will be used with different imputation strategies applied to calculated LDL-C values missing during the on-treatment period (ie, within the time period from the first double blind IMP injection up to the day of last injection +21 days) versus calculated LDL-C values missing after treatment discontinuation (ie, after the day of last injection +21 days) based on the following assumptions:

- Patients within 21 days of their last blind IMP injection would continue to show benefit from treatment similar to that observed at the scheduled time point. Therefore, calculated LDL-C values missing during the on-treatment period (eg., samples obtained out-side the specified window, no blood sample available although visit was performed, etc.) should be considered "Missing At Random" and imputed based on other on-treatment measurements.
- Patients who stopped taking their study treatment no longer benefited from it after discontinuation, and thus tended to have calculated LDL-C values returning to baseline. Therefore, calculated LDL-C values missing more than 21 days after treatment discontinuation should be imputed based on patient's own baseline value.

Missing calculated LDL-C values will be imputed 100 times to generate 100 complete data sets. The percent change from baseline to Week 24 will be derived from observed and imputed calculated LDL-C at this time point. The completed data sets will be analyzed using an ANCOVA model with treatment group and randomization strata (as per IVRS) as fixed effects, and the baseline calculated LDL-C value as continuous covariate. The model for assessing the treatment effect by diabetes type will include an additional interaction: the treatment group-by-strata interaction. The results from the 100 analyses will be combined using Rubin's formulae (6).

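### At the first-step analysis, the SAP's rule for ongoing patients applies to almost nobody still on treatment, and gives anyone it catches at least about 26 weeks of exposure against a 24-week maximum

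*SAP*

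**What the plan says.** SAP section 3 makes the efficacy analysis final at the first step. Safety is analysed on "safety data collected up to the common cut-off date, defined as the date of the last Week 24 visit" and updated at a second step.

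For the first step it adds: "Patients without end of treatment visit performed at the time of the cut-off date will be considered as ongoing and exposed" up to that date. Three sub-bullets follow:

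- Disposition: "Patients who did not complete treatment period nor prematurely discontinued the study treatment at cut-off date will be analyzed as" ongoing.
- Their TEAE, treatment and on-study periods end at the cut-off.
- Exposure: "Their treatment duration will be derived by considering date of cut-off as last injection date" (and as last capsule date).

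The same section takes injection counts, injection frequency and compliance from what the e-CRF reports. It limits the follow-up and last-contact summaries to patients who completed or prematurely discontinued treatment.

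Other sections that bear on this:

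- **SAP 2.5.1** takes the date of last dose from the e-CRF administration page, or leaves it missing.
- **SAP 2.5.3** says: "If the last injection date is missing, then this date is imputed to the earliest between" the end of the known month or year, the EOT visit and the last contact. This serves the analysis periods only; exposure duration stays missing.
- **Protocol 10.3.5**, on withdrawal from the study, says: "If possible, the patients are assessed using the procedure normally planned for the EOT visit". The visit can therefore be absent.
- **Protocol 10.3.4** has definitive treatment discontinuation recorded in the CRF, separately from any visit.

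**The concern.** The rule uses a missing EOT visit as the sign that a patient is still being treated. That works for a data cut taken mid-study. Here the cut-off is the last Week 24 visit, and the last planned injection is two weeks before a patient's own Week 24, so essentially nobody is still due an injection. The rule then falls mainly on patients who left without the visit, and on any who were fully treated but missed Week 24.

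For these patients, exposure duration would include time when no drug was taken. For those without an event, the TEAE period is both the patient-year denominator and the Kaplan-Meier censoring time (SAP 2.4.6.1). Someone lost early could be counted as observed and event-free until the cut-off, which lowers first-step event rates.

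There is also a possible efficacy consequence. If the extended treatment period is taken to be the efficacy treatment period, LDL-C sampled off treatment could enter the on-treatment endpoints, which include the first key secondary. The second step updates safety only, so it would not correct this.

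**Working it through.** **Inputs**

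- Exposure in weeks = (last injection + 14 days − first injection)/7 (SAP 2.4.4).
- Day 1 = first injection; last planned injection at Week 22 = Day 155; Week 24 = Day 169; TEAE period = last injection + 70 days.
- Alirocumab arm: 333 patients (SAP 1.1).
- R = weeks between a caught patient's first dose and that of the last patient, whose Week 24 visit sets the cut-off. R is taken as 0 or more. The documents give a recruitment end (summer 2016) but no start, so R is assumed to run from 0 to 52.

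**Reproducing the plan's own figures.** A patient treated as planned has (155 + 14 − 1)/7 = 24.0 weeks of exposure. The TEAE period ends on Day 155 + 70 = Day 225, which is Week 32. Both match.

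**Exposure under the first-step rule.** If the last patient is seen on Day 169, the cut-off falls on the caught patient's Day 169 + 7R. Exposure = (169 + 7R + 14 − 1)/7 = 26 + R weeks.

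| R (weeks) | Cut-off, patient's study day | Credited exposure (weeks) |
|---|---|---|
| 0 | 169 | 26 |
| 13 | 260 | 39 |
| 26 | 351 | 52 |
| 52 | 533 | 78 |

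The ±3-day visit window moves these by less than half a week (3/7 = 0.4).

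**Exposure from the actual last injection**

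| Last injection (day) | Exposure (weeks) | TEAE end (day) |
|---|---|---|
| 1 | 2 | 71 |
| 57 | 10 | 127 |
| 99 | 16 | 169 |
| 155 | 24 | 225 |

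Credited exposure is too long in every case. The TEAE period is stretched only when last injection + 70 days falls before the cut-off, that is, when the last injection came before Day 99 + 7R. A fully treated patient who missed Week 24 is affected on the TEAE period only if R exceeds 8.

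**Aggregate illustration (assumptions).** Of the 333 patients, a fraction f is caught, each last injected on Day 57. All others have a TEAE period to Day 225 and 24 weeks of exposure.

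- Patient-days with actual dates: 333 × [(1 − f) × 225 + f × 127].
- Under the rule: 333 × [(1 − f) × 225 + f × (169 + 7R)].

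| f | R | Patient-years, actual | Patient-years, rule | Rise | Mean exposure, actual → rule (weeks) |
|---|---|---|---|---|---|
| 1% | 0 | 204.2 | 204.6 | 0.2% | 23.86 → 24.02 |
| 1% | 52 | 204.2 | 207.9 | 1.8% | 23.86 → 24.54 |
| 5% | 0 | 200.7 | 202.6 | 1.0% | 23.30 → 24.10 |
| 5% | 52 | 200.7 | 219.2 | 9.2% | 23.30 → 26.70 |

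In all four rows the mean exceeds the 24-week maximum.

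**Efficacy, by comparing sections.** Section 3 extends the *treatment period*. On-treatment endpoints use the *efficacy treatment period*, which ends 21 days after the last injection (SAP 2.1.4). The SAP blurs the two: SAP 2.3.1.2 speaks of the treatment period and then gives the efficacy definition, and SAP 2.4.6 refers the treatment period back to 2.1.4. Take a last injection on Day 29 and a Week 8 sample on Day 57. The sample is 28 days after the last injection, so it is off treatment under SAP 2.1.4 but on treatment if the period runs to the cut-off.

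**The case against.** The strongest reply is about scope. The first sub-bullet names patients who neither completed nor prematurely discontinued, and *their* in the next two most naturally refers to that group. The later bullets make the same contrast. Since definitive discontinuations go into the CRF whether or not a visit occurs, and the first step waits for validated data to Week 24, the group may be nearly empty. This stands as a plausible reading, but the opening sentence has no such limit, so a programmer could follow either. The narrower reading still catches losses with no discontinuation record.

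A reader might go further than the documents allow in five ways:

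- **That only lost, withdrawn or dead patients are caught.** A fully treated patient who missed Week 24 is caught too. If the cut-off is taken as the visit of the last patient randomised, the visit window could leave a few others unseen.
- **That patients are credited with injections.** Counts, frequency and compliance stay with the e-CRF.
- **That SAP 2.5.3 is contradicted outright.** It is triggered by an unknown date, section 3 by a missing visit. They collide only where both apply.
- **That the pattern-mixture check is disabled.** SAP 2.4.5.1.3 says "calculated LDL-C values missing more than 21 days after treatment discontinuation should be imputed based on" the patient's own baseline, and splits at the last injection + 21 days. SAP 2.5.1 takes that date from the e-CRF, and section 3 replaces it only when deriving treatment duration. Misclassification is possible, not shown.
- **That on-treatment efficacy is certainly contaminated.** Section 3 does not name the efficacy treatment period. A patient would also have to stop, keep giving samples and have no EOT visit. The primary ITT analysis does not use the treatment period.

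Safety is re-analysed at the second step, so distortion there is temporary.

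**Conclusion.** The point holds as a defect of wording that produces wrong results for whoever it catches. With the cut-off set at the last Week 24 visit, the ongoing category should contain essentially nobody on treatment. Anyone placed in it is given 26 + R weeks of exposure against a maximum of 24, and the TEAE period runs to the cut-off regardless of the actual last injection or contact. The opening sentence and the first sub-bullet disagree on who is included.

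The overall size is uncertain. The 0.2% to 9.2% rise in TEAE patient-years rests on assumed values for the fraction caught (1% to 5%), R (0 to 52 weeks) and the last injection (Day 57); if recorded discontinuers are exempt, the fraction may be well below that range. The consequence for final efficacy results depends on how *treatment period* is read, and for the pattern-mixture split it is not established. The ambiguity is worth closing because efficacy is not revisited after this step.

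**What to change.** In SAP section 3, before the first-step database lock:

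1. Apply the ongoing rule only to a patient with no EOT visit, no recorded discontinuation, withdrawal, death or loss of contact, and a planned Week 24 date after the cut-off.
2. For everyone else, use the e-CRF last injection date for exposure and for the treatment and TEAE periods. If that date is unknown, use the SAP 2.5.3 imputation for the analysis periods only and leave exposure duration missing.
3. State that the efficacy treatment period and the pattern-mixture split always use this same date.
4. Delete the capsule wording, since the study treatment is given only by injection.

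The cost is a few sentences and a little programming. Mean exposure at the first step would be slightly lower.

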	
Alirocumab will be administered subcutaneously with a starting dose of 75 mg every 2 weeks (Q2W) for 12 weeks with a blinded uptitration to alirocumab 150 mg Q2W at Week 12 if the LDL-C at the Week 8 visit is ≥ 70 mg/dL (1.81 mmol/L). Patients who have an LDL-C < 70 mg/dL (1.81 mmol/L) at the Week 8 visit will continue with alirocumab 75 mg every two weeks until the end of the double-blind treatment period.
 
The study consists of:
 
• A screening period of up to 3 weeks;• A double-blind treatment period of 24 weeks;• A safety observation period (off-treatment) of 8 weeks after the end of the double-blind treatment period. 
Note, the Investigator will need to document in the case report form (CRF) any adverse events (AEs) that have occurred within 70 days of the last dose of IMP that (s)he is aware of. A phone visit will take place at Week 32 in order to ensure documentation of any AEs occurring during this period.
 
Patients should be on a stable diet for glucose and lipid management throughout the entire study duration from screening to the Week 24 visit. There shall be no significant changes in nutritional composition of the diet or in the quantity/pattern of food consumed. Patients must be receiving treatment for diabetes in accordance with local/regional standards of care.
 
Statin dose and dose regimen as well as dose and dose regimen of other lipid modifying treatment(s) (if applicable) should be stable for 4 weeks prior to the screening period and throughout the entire study duration, including from the screening visit to randomization.
 
The data on lipid parameters from blood samples will be masked after randomization. No attempts should be made by the Investigator or patient to have the patient's lipid values independently evaluated after randomization until after the Week 24 visit, except for the safety of the patient as per the Investigator's judgment. At the end of the double-blind treatment period (Week 24 visit), the Investigator will continue to manage the patient's lipids in accordance with standard practice. Any lipid values after randomization (eg, if done for patient safety) should be redacted in the source documents and not shared with the Sponsor.
 
Duration of study treatment will be 24 weeks with the last injection administered at Week 22.
 
Patients will visit the study site at Weeks -3, 0, 8, 12, 20, and 24 with lab work at each visit; in addition phone visits are scheduled at Weeks 4 and 32. Week 8 is a critical visit because it will be the only scheduled visit where an LDL-C value for uptitration will be available.

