ASSESSMENT SCHEDULE	
V1: (Week -3 [Day -21 to -8]): screening, investigational medicinal product (IMP) training, and safety.
 
V2: (Week 0 [Day 1 ±3 days]): baseline, randomization, first administration with double-blind IMP, and safety.
 
V3: (Week 4 [Day 29 ±7 days]): telephone contact
 
V4: (Week 8 [Day 57 ±3 days]); V5: (Week 12, [Day 85 ±3 days]); V6: (Week 20 [Day 141 ±7 days]) (efficacy and safety assessments)
 
V5: (Week 12) Second allocation of double-blind IMP
 
V7: (Week 24 [Day 169 ±3 days]): End of treatment (EOT) visit (efficacy and safety assessments)
 
V8: (Week 32 [Day 225 ±7 days]): telephone contact (safety assessment)
 
If one visit is changed, the next visit should take place according to the original schedule. Note: Patients who prematurely discontinue treatment should be followed as scheduled.

STATISTICAL CONSIDERATIONS	
Sample size determination:
  
Analysis Population:
 
Randomized population includes any patients who have been allocated to a randomized treatment regardless of whether the treatment kit was used or not.
 
The primary efficacy analysis population will be the ITT population, defined as all randomized patients who had an evaluable primary efficacy endpoint.
 
The primary efficacy endpoint will be considered evaluable when both of the following conditions are met:
 
• The baseline calculated LDL-C value is available• At least one calculated LDL-C value is available within one of the analysis windows up to Week 24. 
The mITT population (otherwise referred to as the on-treatment population) is defined as all randomized patients who took at least one dose or part of dose of the double-blind IMP injection and had an evaluable primary efficacy endpoint during the efficacy treatment period.
 
The primary efficacy endpoint will be considered evaluable during the efficacy treatment period when both of the following conditions are met:
 
• The baseline calculated LDL-C value is available

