The incidence of premature treatment discontinuation (irrespective of the reason) and premature treatment discontinuation due to AEs will be presented graphically by treatment group on randomized and treated patients (as randomized), using Kaplan-Meier method.

The incidence of premature study discontinuation (irrespective of the reason) and premature study discontinuation due to AEs will be presented graphically by treatment group on randomized and treated patients (as randomized), using Kaplan-Meier method.

Patients with insufficient post-treatment follow-up will be described on the safety population by treatment group. A patient is considered with insufficient post-treatment follow-up or without post-treatment follow-up at the end of the study in the following cases:

- If the patient is not assessed at the post-treatment follow-up call or any post-treatment visit, unless patient died before, or
- If the last post-treatment visit is less than 9 weeks after the last double-blind injection.

All major deviations potentially impacting efficacy analyses, randomization, and drug-dispensing irregularities, and other major or critical deviations will be summarized in tables giving numbers and percentages of deviations by treatment group. Patients excluded from the ITT/mITT population will be listed as well as patients with major deviations potentially impacting efficacy analyses not resulting in exclusion from ITT/mITT population. These deviations are listed in the data review and surveillance plan.

Additionally, the following analysis populations will be summarized by treatment group:

- Randomized population;
- Efficacy population: ITT population and mITT;
- Safety population;
- [REDACTED]
- ADA population.

Definitions of the study populations are provided in [Section 2.3](#).

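### At the first-step analysis, patients who finished treatment recently count as insufficiently followed before their Week 32 call is due

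*SAP*

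**What the plan says.** SAP section 2.2 (Disposition of patients) defines the measure by reference to study end: "A patient is considered with insufficient post-treatment follow-up or without post-treatment follow-up at the end of the study in the following cases". Two conditions follow. The first is "If the patient is not assessed at the post-treatment follow-up call or any post-treatment visit, unless patient died before, or". The second is "If the last post-treatment visit is less than 9 weeks after the last double-blind injection".

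SAP section 3 (Interim analysis) schedules the same measure at the first step: the "proportion of patients with insufficient follow-up will be provided for patients who either completed or prematurely discontinued the treatment" by the cut-off. That step uses safety data up to a "common cut-off date, defined as the date of the last Week 24 visit". The only patients set aside are those with no end-of-treatment visit by then, who are treated as ongoing. No minimum time since the last injection is required, and there is no category for patients whose follow-up is still running.

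The timetable is in the protocol. The synopsis states: "Duration of study treatment will be 24 weeks with the last injection administered at Week 22". The assessment schedule gives "V7: (Week 24 [Day 169 ±3 days]): End of treatment (EOT) visit" and places the Week 32 telephone contact at Day 225 ±7 days. Protocol section 10.1.2.5 describes that contact as 10 weeks after the last injection.

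**The concern.** Section 3 draws its line at the end of treatment, but the 9-week condition can only be judged several weeks later. Patients in between have completed treatment and are not ongoing, yet cannot have had a contact late enough to satisfy section 2.2. They would enter the table as insufficiently followed however well the sites performed.

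The first-step figure would then depend largely on how many patients were enrolled near the end of recruitment, rather than on the quality of follow-up. The protocol (sections 6.3 and 11.5) foresees a Week 24 analysis for scientific communication, so the figure could be quoted before the second step replaces it.

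**Working it through.** **Inputs.** Last injection at Week 22; end-of-treatment visit on Day 169 ±3; Week 32 call on Day 225 ±7 (protocol synopsis and flow chart). Injection window ±3 days (protocol 8.1.2). Nine-week condition, 63 days (SAP 2.2). Cut-off at the last Week 24 visit (SAP 3). First lock 30 working days later (SAP 4). Study day = 7 × week + 1.

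**The plan's own figure.** Last injection: 7 × 22 + 1 = Day 155. Call: 7 × 32 + 1 = Day 225. Difference: 225 − 155 = 70 days, or 10 weeks, as the protocol states.

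**Earliest qualifying contact.** 155 + 63 = Day 218, which is also the first day of the call window (225 − 7). Measured from the end-of-treatment visit:

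- 9-week condition reachable: 218 − 169 = 49 days, or 7 weeks.
- Nominal call: 225 − 169 = 56 days, or 8 weeks.

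A surviving on-schedule completer whose Week 24 visit was less than 7 weeks before the cut-off must meet the definition. Between 7 and 8 weeks the outcome depends on whether the call was made early in its window. Counting the Week 24 visit as a post-treatment visit does not help: 169 − 155 = 14 days, short of 63.

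**Effect of the windows.** With ±3 days on both the injection and the visit, the 7 weeks ranges from (152 + 63 − 172)/7 = 6.1 to (158 + 63 − 166)/7 = 7.9 weeks.

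**Early stoppers.** Someone whose last injection was under 63 days before the cut-off is caught in the same way. Someone whose last injection was on or before Day 106 (169 − 63) and who attends Week 24 on Day 169 satisfies the condition and is not caught.

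**If contacts up to lock count.** Thirty working days is about 42 calendar days. The affected span falls to 49 − 42 = 7 days, or 56 − 42 = 14 days at the nominal call date: 1 to 2 weeks.

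**Share of patients.** Recruitment length R is not in the documents, so even accrual over a range of R is assumed, with 500 patients who all complete on schedule. Share = 7/R to 8/R for contacts up to the cut-off, and 1/R to 2/R for contacts up to lock.

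| R (weeks, assumed) | Contacts to cut-off | Of 500 | Contacts to lock |
|---|---|---|---|
| 26 | 26.9–30.8% | 135–154 | 3.8–7.7% |
| 39 | 17.9–20.5% | 90–103 | 2.6–5.1% |
| 52 | 13.5–15.4% | 67–77 | 1.9–3.8% |
| 65 | 10.8–12.3% | 54–62 | 1.5–3.1% |

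**The case against.** The best defence is that section 2.2 ties the classification to the end of the study, and that section 3 carries other conventions over only as applicable. A careful programmer might leave patients awaiting their call unclassified. This shows that the two sections conflict, but it does not settle the conflict: section 3 expressly orders the proportion at the first step and excludes only ongoing patients.

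A second defence concerns later contacts. Section 3 lists what is dropped after the cut-off (adverse events, medications, treatment discontinuations and completions, deaths), and follow-up contacts are not on that list. Against this, the first-step safety analysis uses data up to the cut-off. The point stands as an ambiguity, which is why both ranges are given. Even on the favourable reading, the last 1 to 2 weeks of completers are still caught.

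A reader might infer more than the documents support:

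- *Genuine losses would be hidden.* SAP 2.2 separately tabulates study discontinuations with reasons and status at last contact, and plots study discontinuation by Kaplan-Meier. Those losses remain visible.
- *A false difference between Type 1 and Type 2 would appear.* SAP 2.2 specifies this output by treatment group. The general sentence in SAP 2.4.6 could extend it to diabetes type, and the two types have separate recruitment rules, but no closing dates are given. The contrast is conjecture.
- *The arms would be distorted.* Randomization is 2:1 within diabetes type, so late accrual should fall on both arms in proportion.
- *Status at last contact has the same defect.* It is meaningful for anyone at the cut-off; no defect is shown.

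**Conclusion.** The concern holds as a small correction. As written, the first-step rule counts surviving on-schedule completers from about the last 7 weeks before the cut-off (up to 8 if not called early), and patients whose last injection was under 9 weeks before it, as insufficiently followed when no call is yet due. The 7 and 8 weeks follow from the documents' own visit days.

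The percentages rest on assumed even accrual. Over 26 to 52 weeks they are about 13–31% with contacts to the cut-off and about 2–8% with contacts to lock. Extending accrual to 65 weeks lowers the bottom of these ranges to about 11% and 1.5%.

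The effect is confined to one descriptive first-step output. No efficacy estimate, type I error or comparison between arms changes, and the second step updates the safety analysis to Week 32.

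**What to change.** Add one sentence to the first-step rules in SAP section 3. Compute the insufficient follow-up proportion only for patients whose follow-up call window had closed by the cut-off, or who had left the study by then, and show the others in a row labelled as follow-up not yet due. For an on-schedule completer, a closed window means a last injection at least 70 + 7 = 77 days before the cut-off (Day 155 + 77 = Day 232, the last day of the call window). For patients who stopped early but kept to the visit schedule under protocol 10.3.4, use the date of their own scheduled call. State also whether contacts between the cut-off and database lock count.

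Alternatively, produce this output only at the second step, which fits the end-of-study wording in section 2.2. Leave status at last study contact unchanged.

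The cost is one sentence, one extra table row and a smaller first-step denominator.
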